12.6 Early Withdrawal Visit

In the case that the patient withdraws or is withdrawn from the protocol (see Section 14) before the end of the intervention period, and providing the patient consents, then the investigators will perform and record the participant's MEP, MIP, thickness of the abdominal wall muscles and diaphragm, CPF, resting breathing parameters and adverse events related to stimulation or otherwise.

If the participant is withdrawn from the study because they have successfully weaned from mechanical ventilation then the study researcher will also calculate and record the number of days taken to wean taken from the institution of mechanical ventilation.

13 Adverse Experience Reporting and Documentation

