11.15 Measures of Treatment Compliance

The study treatment devices will automatically record the date, time and duration of stimulation for an individual patient to a memory card.

12 Study Schedule

A Schedule of Events representing the required testing procedures to be performed for the duration of the study is diagrammed in Appendix 1. A description of each procedure is provided in Section 11

Prior to conducting any study-related activities, written informed consent and the Health Insurance Portability and Accountability Act (HIPAA) authorization must be signed and dated by the participant.

12.1 Baseline Visit - Day 1

On day 1 the investigators will review the study with the participant and obtain written informed consent and HIPAA authorization. After consent has been obtained they will record the patient's demographic data, medical history and concomitant medications.

The investigators will determine if the patient meets the study inclusion and exclusion criteria. If the patient does not meet the criteria then no further procedures will be performed and they will be withdrawn from the study. If the patient does meet the criteria then the investigator will randomize the patient to a treatment group.

The study researcher will record their vital signs, oximetry, expiratory flow limitation, APACHE II score, MIP, MEP, thickness of the abdominal wall muscles and diaphragm, CPF and resting breathing parameters.

12.2 Stimulation Visits – Days 2 - 22

Patients will participate in Stimulation Visits two 2 per day in 5 days every week. Specifically, patients will participate in morning and afternoon Stimulation Visits 5 times between days 2 and 8, 5 times between days 9 and 15 and 5 times between days 15 and 22.

The investigators will administer sixty minutes of stimulation to the participant as described in Section 9.6. In addition, the investigators will record adverse events related to stimulation or otherwise.

12.3 Intermediate Visit – Day 23

The Intermediate Visit will ideally take place on day 21. However, if necessary the Intermediate Visit may be conducted no earlier than day 20 and no later than day 25, providing that it occurs after 15 Stimulation Visits.

At the start of the visit the investigators will measure MEP, MIP, CPF, thickness of the abdominal wall muscles and diaphragm, resting breathing parameters, changes to medications and adverse events related to stimulation or otherwise.

12.4 Stimulation Visits – Days 24 – 44

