14.1 Withdrawal of Participants from the Study

A participant may be withdrawn from study treatment at any time if the participant, the investigator, or the Sponsor feels that it is not in the participant's best interest to continue. The following is a list of possible reasons for study treatment discontinuation:

- Successful weaning from mechanical ventilation
- Participant withdrawal of consent
- Participant is not compliant with study procedures
- Adverse event that in the opinion of the investigator would be in the best interest of the participant to discontinue study treatment
- Protocol violation requiring discontinuation of study treatment
- Lost to follow-up
- Sponsor request for early termination of study
- Positive pregnancy test (females)

If a participant is withdrawn from treatment due to an adverse event, the participant will be followed and treated by the PI until the abnormal parameter or symptom has resolved or stabilized.

All participants who discontinue study treatment should come in for an early discontinuation visit as soon as possible.

All participants are free to withdraw from participation at any time, for any reason, specified or unspecified, and without prejudice. This will not affect the care they receive, now or in the future.

Reasonable attempts will be made by the investigator to provide a reason for participant withdrawals. The reason for the participant's withdrawal from the study will be specified in the participant's source documents.

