22 APPENDIX A: SCHEDULE OF EVENTS

	Baseline Day 1	Stimulation Visits Days 2 - 22	Intermediate Visit Day 23	Stimulation Visits Days 24 - 44	Final Visit Day 45	Early Withdrawal
Informed Consent	X					
Randomization	X					
Medical History	X					
Concomitant Medications	X		X		X	X
Complete Physical Exam	X					
Height	X					
Weight	X					
Vital Signs	X					
Oximetry	X					
Expiratory Flow Limitation	X					
APACHE II	X					
Maximum Expiratory Pressure	X		X		X	X
Maximum Inspiratory Pressure	X		X		X	X
Abdominal Wall Thickness	X		X		X	
Diaphragm Thickness	X		X		X	
Cough Peak Flow	X		X		X	X
Tidal Volume	X		X		X	X
Respiratory Rate	X		X		X	X
Minute Ventilation	X		X		X	X
Administration of Stimulation		X		X		
Sensation of Stimulation		X		X		
Adverse Events	X	X	X	X	X	X
Time spent breathing without mechanical ventilation support	X	X	X	X	X	X
Number of Days Taken to Wean						X

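### Section 12.6 requires abdominal wall and diaphragm thickness at the Early Withdrawal Visit, but Appendix A leaves both unmarked there, putting the exit value of this secondary outcome at risk

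*Combined protocol and SAP*

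**What the plan says.** Section 12.6 covers participants who withdraw or are withdrawn before the intervention period ends and who consent to the visit. After MEP and MIP, it lists "thickness of the abdominal wall muscles and diaphragm, CPF, resting breathing parameters and adverse events related to stimulation or otherwise". The same section treats successful weaning as one reason for withdrawal and has the number of days to wean recorded then.

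Appendix A has rows for "Abdominal Wall Thickness" and "Diaphragm Thickness". Both carry marks at Baseline, Intermediate (Day 23) and Final (Day 45), with nothing under Early Withdrawal. The row for "Cough Peak Flow" has all four marks, as do MEP, MIP, tidal volume, respiratory rate and minute ventilation. The row "Number of Days Taken to Wean" is marked under Early Withdrawal only.

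Section 12 introduces the grid in these words: "A Schedule of Events representing the required testing procedures to be performed for the duration of the study is diagrammed in Appendix 1". The grid is in fact headed Appendix A.

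Section 14.1 puts "Successful weaning from mechanical ventilation" first among the reasons for stopping study treatment and asks everyone who stops to attend an early discontinuation visit. Section 6 ends treatment at six weeks or at weaning, whichever comes first, and plans evaluations at baseline, at three weeks and when treatment ends. Section 7.2 names both thickness measures as secondary outcomes.

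**The concern.** In many trials the early withdrawal visit serves a few dropouts. Here it is also the planned exit for participants who succeed. A measurement missing from that column is therefore missing in a way tied to weaning, itself a secondary outcome that the device is meant to influence.

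If staff follow the grid, thickness at the end of treatment is observed mainly in those still ventilated at Day 45. If the device speeds weaning, the active arm would lose more participants from that comparison than the control arm.

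The analysis text adds to the difficulty. Section 17 places the regression models at the time of successful weaning, which for an early weaner is the visit where the grid schedules no thickness. It also limits the analysis to participants who meet the protocol on outcome assessment. With two conflicting statements of what must be assessed, it is unclear whether someone measured according to the grid qualifies. An ultrasound not done at exit cannot be recovered later.

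**Working it through.** **Consistency check.** The requirements at Early Withdrawal, side by side:

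| Measure | Section 12.6 | Appendix A, Early Withdrawal |
|---|---|---|
| MEP, MIP | required | marked |
| Cough peak flow | required | marked |
| Resting breathing (three rows) | required | marked |
| Abdominal wall thickness | required | blank |
| Diaphragm thickness | required | blank |

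Lost marks in text extraction are an unlikely explanation: the rows directly above and below keep their last mark, and both thickness rows show the same gap.

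Section 11 does not settle the matter. Sections 11.10 and 11.11 name only Baseline, Intermediate and Final for thickness, but sections 11.9 and 11.12 do the same for MEP, MIP and cough peak flow, which the grid does mark at Early Withdrawal. Section 6 does help: for someone who weans early, treatment ends at weaning, so its end-of-treatment evaluation falls at the early visit. Sections 6 and 12.6 agree, and the grid is the outlier.

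**What is lost if the grid is followed.**

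- Leaves before the Intermediate Visit: baseline only, no post-baseline thickness.
- Leaves after the Intermediate Visit but before the Final Visit: baseline and Day 23, no exit value.
- Reaches the Final Visit: all three values.

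**How many.** The documents give no figure for this. Section 17.1 gives 24 participants as adequate (12 per arm in section 6) and 26 recruited to allow for 10% dropout. As a check, 24/0.9 = 26.67, close to the stated 26; the point does not depend on it. No weaning rate is given, so let w be an assumed proportion weaning early, equal in both arms. The number without an exit value is 24w, the number left per arm is 12(1 − w), and the standard error of the exit comparison is multiplied by 1/√(1 − w).

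| Assumed w | Without exit value (of 24) | Left per arm | SE multiplier |
|---|---|---|---|
| 25% | 6 | 9 | 1.15 |
| 50% | 12 | 6 | 1.41 |
| 75% | 18 | 3 | 2.00 |

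These counts cover early weaners only. Other withdrawals would add to them.

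**Possible bias.** A simulation with every input assumed: thickness change is normal with SD 1 and a true arm difference of 0.50 SD; a latent tendency to wean has correlation ρ with thickness change; a common threshold gives 30% or 50% weaning in the control arm; only the non-weaned are analysed.

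| ρ | Control weaning 30% | Control weaning 50% |
|---|---|---|
| 0 | 0.50 | 0.50 |
| 0.3 | 0.48 | 0.47 |
| 0.5 | 0.43 | 0.42 |

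In this model the observed difference shrinks modestly when thickness gain and weaning are linked, and not at all when they are not. Another link between arm, weaning and thickness could give a different size or direction.

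**The case against.** The strongest reply is that the text already requires the measurement. Section 12.6 states it, section 6 implies it, and only a summary grid omits it. The grid is also incomplete elsewhere: sections 11.5 and 11.6 call for vital signs and oximetry at the Intermediate and Final Visits, yet Appendix A marks them at Baseline only. That suggests a clerical gap rather than a decision to stop measuring thickness in those who wean. This stands. The point is an internal inconsistency and not a flaw in the intended design, and any loss depends on staff following the grid over the text. It does not dispose of the matter, because section 12 gives the grid the status of required procedures and staff may well work from it.

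A reader might infer that every weaned participant loses this outcome, or that exactly the successes do. The documents support neither:

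- Section 14.1 also sends participants who stop for adverse events, non-compliance or other reasons to the early visit.
- Someone who weans at the very end of the six weeks could be measured at the Final Visit.
- Only the exit value is at risk. Baseline stays for all, and Day 23 stays for later leavers.

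It is also fair to say that thickness is a secondary outcome in a pilot without a power calculation, and that the simulated attenuation is small.

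**Conclusion.** The contradiction between section 12.6 and Appendix A is certain, and the two must be reconciled. Its consequence is conditional. If the grid is followed, exit thickness is missing for those who leave before Day 45, mostly but not only people who weaned, and the remaining end-of-treatment values come mainly from those still ventilated. *Mostly* rests on the plan's own use of this visit: weaning heads the list of reasons for stopping, and days to wean is recorded in that column alone.

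The documents do not let the loss be sized. The range of 6 to 18 of 24 is arithmetic on an assumed 25% to 75% weaning early, and the simulated 0.42 to 0.48 SD against a true 0.50 rests wholly on assumed inputs. Neither should be read as a forecast. The correction is worth making before enrolment because the missing value cannot be recovered and the change is very small; it does not call the primary outcome into question, since MEP and MIP are marked at Early Withdrawal.

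**What to change.** In Appendix A, mark Abdominal Wall Thickness and Diaphragm Thickness in the Early Withdrawal column, so that the grid agrees with section 12.6 and with the end-of-treatment evaluation in section 6. The reference in section 12 to Appendix 1 can be corrected at the same time.

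The cost is two table cells and a cross-reference. No procedure is added beyond what section 12.6 already requires, and neither treatment nor the analysis methods change.

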13.1 Adverse Events

An adverse event (AE) is any untoward medical occurrence in a clinical investigation of a patient administered an investigational product and that does not necessarily have a causal relationship with the treatment. An AE is therefore any unfavorable and unintended sign (including an abnormal laboratory finding), symptom or disease temporally associated with the administration of an investigational product, whether or not related to that investigational product. An unexpected AE is one of a type not identified in nature, severity, or frequency in the current Investigator's Brochure (attached) or of greater severity or frequency than expected based on the information in the Investigator's Brochure.

The Investigator will probe, via discussion with the participant, for the occurrence of AEs during each participant visit and record the information in the site's source documents. AEs will be recorded in the patient CRF. AEs will be described by duration (start and stop dates and times), severity, outcome, treatment and relation to study device or if unrelated, the cause.

AE Severity

The National Cancer Institute's Common Terminology Criteria for AEs (CTCAE) Version 3.0 should be used to assess and grade AE severity, including laboratory

abnormalities judged to be clinically significant. The guidelines shown in **Table 1** below should be used to grade severity. It should be pointed out that the term "severe" is a measure of intensity and that a severe AE is not necessarily serious.

Table 1 AE Severity Grading

Severity (Toxicity Grade)	Description
Mild (1)	Transient or mild discomfort; no limitation in activity; no medical intervention or therapy required. The participant may be aware of the sign or symptom but tolerates it reasonably well.
Moderate (2)	Mild to moderate limitation in activity, no or minimal medical intervention/therapy required.
Severe (3)	Marked limitation in activity, medical intervention/therapy required, hospitalizations possible.
Life-threatening (4)	The participant is at risk of death due to the adverse experience as it occurred. This does not refer to an experience that hypothetically might have caused death if it were more severe.

AE Relationship to Study Device

The relationship of an AE to the study device should be assessed using the following the guidelines in **Table 2**

Table 2 AE Relationship to Study Device

Relationship to Device	Comment
Definitely	Previously known adverse event; or an event that follows a reasonable temporal sequence from administration of the device; that follows a known or expected response pattern to the suspected device; that is confirmed by stopping administration of the device; and that is not explained by any other reasonable hypothesis.
Probably	An event that follows a reasonable temporal sequence from administration of the device; that follows a known or expected response pattern to the suspected device; that is confirmed by stopping the administration of the device; and that is unlikely to be explained by the known characteristics of the participant's clinical state or by other interventions.
Possibly	An event that follows a reasonable temporal sequence from administration of the device; that follows a known or expected response pattern to that suspected device; but that could readily have been produced by a number of other factors.
Unrelated	An event that can be determined with certainty to have no relationship to the study device.

13.2 Serious Adverse Experiences (SAE)

An SAE is defined as any AE occurring at any dose that results in any of the following outcomes:

- death
- a life-threatening adverse experience
- inpatient hospitalization or prolongation of existing hospitalization

- a persistent or significant disability/incapacity
- a congenital anomaly/birth defect

Other important medical events may also be considered an SAE when, based on appropriate medical judgment, they jeopardize the participant or require intervention to prevent one of the outcomes listed.

13.2.1 Serious Adverse Experience Reporting

Study sites will document all SAEs that occur (whether or not related to study device). The collection period for all SAEs will begin after informed consent is obtained and end after procedures for the final study visit have been completed.

In accordance with the standard operating procedures and policies of the local Institutional Review Board (IRB)/Independent Ethics Committee (IEC), the site investigator will report SAEs to the IRB/IEC.

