Each participant will receive either active or placebo electrical muscle stimulation to the abdominal wall during exhalation for sixty minutes per day, five days per week for the shorter of six weeks or until the patient is weaned from mechanical ventilation. Participants will be assigned to active or placebo stimulation in random order (using a random number generator). Evaluations will be performed at baseline, after three weeks of treatment and at the end of treatment. A flow diagram of the study protocol is shown in Figure 3

[figure not shown]

Figure 3 Study Flow Diagram

The maximum duration of participant participation is 45 days. The total duration of the study is expected to be 6 months.

7 Outcome Measures

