11.14 Adverse Events

Information regarding occurrence of adverse events will be captured throughout the study. Duration (start and stop dates and times), severity/grade, outcome, treatment and relation to study device will be recorded on the case report form (CRF).

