12.3 Replacement of Participants

While it is estimated that 24 is a suitable sample size for this study, the actual study sample size of 26 allows for a 10% drop out rate. Therefore, up to two participants who withdraw from the study will be replaced.

15 Protocol Violations

A protocol violation occurs when the participant, investigator, or Sponsor fails to adhere to significant protocol requirements affecting the inclusion, exclusion, participant safety and primary endpoint criteria.

Failure to comply with Good Clinical Practice (GCP) guidelines will also result in a protocol violation. The Sponsor will determine if a protocol violation will result in withdrawal of a participant.

When a protocol violation occurs, it will be discussed with the investigator and a Protocol Violation Form detailing the violation will be generated. This form will be signed by a Sponsor representative and the Investigator. A copy of the form will be filed in the site's regulatory binder and in the Sponsor's files.

16 Protocol Amendments

Amendments to the clinical investigation plan must be submitted to the Sponsor for review before submitting to the appropriate IRB for approval.

17 Statistical Methods and Considerations

Only participants who fulfil the protocol in terms of eligibility, interventions and outcome assessment will be included in the statistical analysis. Patient variables will be presented using means and standard deviations for continuous normally distributed variables, medians and interquartile ranges for continuous non-normally distributed variables, and proportions and absolute numbers for categorical variables.

Adverse event rates will be coded by body system and MedDra classification term. Adverse events will be tabulated by treatment group and will include the number of patients for whom the event occurred, the rate of occurrence, and the severity and relationship to study treatment.

Study results will first undergo descriptive level statistical analyses. For continuous variables, Two-way, Student's t-tests will then be carried out using unequal variances where the variables are normally distributed. Tests for normality will be carried out using the Shapiro-Wilk method. Variables that are not normal in distribution that also cannot be log transformed to a normal distribution curve will be analysed using the Mann-Whitney U test or other non-parametric methods to be determined based on actual data distributions.

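### Adverse-event observation in effect ends when a participant weans, and the event rate has no person-time denominator, so the safety table may favour whichever arm weans faster

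*Combined protocol and SAP*

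**What the plan says.** Treatment length depends on weaning. Section 6 sets stimulation at "five days per week for the shorter of six weeks or until the patient is weaned from mechanical ventilation". The first reason listed in Section 14.1 for stopping is "Successful weaning from mechanical ventilation".

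Weaning also ends participation. Section 12.6 has a provision that opens "If the participant is withdrawn from the study because they have successfully weaned from mechanical ventilation". The exit visit is prompt and not tied to Day 45; in Section 14.1, "All participants who discontinue study treatment should come in for an early discontinuation visit as soon as possible". For those who stay, Section 6 states: "The maximum duration of participant participation is 45 days".

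On collection, Section 11.14 says: "Information regarding occurrence of adverse events will be captured throughout the study". Section 13.2.1 adds, for serious events only, that collection will "end after procedures for the final study visit have been completed". Appendix A marks adverse events in every column up to Early Withdrawal and has no contact after it. The only follow-up described beyond withdrawal, in Section 14.1, is for participants withdrawn because of an adverse event, until that problem resolves or stabilises.

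On analysis, Section 17 (repeated in the Synopsis) says that the tabulation by arm "will include the number of patients for whom the event occurred, the rate of occurrence", with severity and relationship to treatment. It does not say whether the rate is per patient, per session or per day. No time-to-event or exposure-adjusted analysis of adverse events is described.

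**The concern.** The long-term goal in the Synopsis is to shorten weaning. The length of safety observation is therefore tied to an outcome that the device is meant to change. If active stimulation works, that arm contributes fewer observed days, and a count of patients with events will tend to be lower there even if the daily risk is the same.

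There is also a gap in capture. Section 7.2 defines weaning success as 72 hours without ventilator support. A death or a return to ventilation after that point and after the exit visit has no scheduled route into the data. The same event in a participant who is still ventilated would be recorded.

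Section 17.1 says the pilot is to supply initial feasibility and safety data, and Section 7.2 lists adverse events as an outcome, so a reader will compare the arms in this table.

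**Working it through.** The plan states no adverse-event rate or weaning rate, so there is no figure of its own to reproduce. The check asks how far the table would move if the two arms had the same daily risk.

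**Inputs**
- From the documents: maximum participation T = 45 days (Section 6); 13 per arm (Synopsis).
- Assumed: a constant adverse-event hazard λ, equal in both arms, from 0.005 to 0.05 per day; exponential time to weaning with median m, so w = ln 2 / m; observation ends at the earlier of weaning or day 45. The 72 hours and the short wait for the exit visit are ignored.

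**Formulas**
- Mean observed days = (1 − exp(−wT)) / w
- P(at least one event) = λ/(λ + w) × (1 − exp(−(λ + w)T))

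**Worked case, λ = 0.02**
- m = 30: w = 0.0231; mean observation 28.0 days; P = 0.02/0.0431 × (1 − exp(−0.0431 × 45)) = 0.397.
- m = 15: w = 0.0462; mean observation 18.9 days; P = 0.02/0.0662 × (1 − exp(−0.0662 × 45)) = 0.287.
- Risk ratio 0.287/0.397 = 0.72, or 3.7 versus 5.2 of 13 patients.

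**Range** (probability of any event; risk ratio against the 30-day arm in brackets)

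| λ per day | 30 days | 25 days | 20 days | 15 days |
|---|---|---|---|---|
| 0.005 | 12.8% (1.00) | 11.8% (0.92) | 10.5% (0.82) | 8.8% (0.69) |
| 0.01 | 23.4% (1.00) | 21.7% (0.93) | 19.4% (0.83) | 16.4% (0.70) |
| 0.02 | 39.7% (1.00) | 37.0% (0.93) | 33.5% (0.84) | 28.7% (0.72) |
| 0.05 | 65.8% (1.00) | 62.4% (0.95) | 57.8% (0.88) | 51.3% (0.78) |

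Where weaning differs, the gap runs from 13 × 0.010 = 0.1 patients (30 versus 25 days, λ = 0.005) to 13 × 0.146 = 1.9 patients (30 versus 15 days, λ = 0.05).

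**Against chance.** For 39.7% versus 28.7%, the standard error of the difference is √(0.397 × 0.603/13 + 0.287 × 0.713/13) = 0.185. That is 18.5 points, against a shift of about 11.

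**After either repair.** Under these assumptions, events per participant-day have an expected ratio of 1.00. Following everyone to day 45 gives 1 − exp(−45λ) in both arms: 20%, 36%, 59% and 90% for the four hazards.

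**If risk falls after weaning.** Take 0.02 per day on the ventilator and 0.01 after. With a = w + λon − λoff, full follow-up gives P = 1 − [exp(−(λon + w)T) + w·exp(−λoff·T)(1 − exp(−aT))/a]. This is 51.2% (m = 30) versus 46.7% (m = 15), a true difference of 4.5 points. Observation cut at weaning would show 39.7% versus 28.7%, or 11.0 points.

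**The case against.** The strongest reply is that Section 13.2.1 can be read as running to the named Final Visit, ideally on Day 45 (Section 12.5), and that Section 14.1 lists weaning as a reason to stop treatment, not necessarily to leave the study. The wording is ambiguous and concerns serious events only. But Section 12.6 speaks of withdrawal from the study, and Appendix A schedules nothing afterwards. On the longer reading, no procedure collects the data for weaned participants. Section 13.3 (Medical Monitoring) was not in the copy available, so relevant text there cannot be ruled out.

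Second, Section 17 does list a rate, so it would be wrong to say that events are reported only per patient. The gap is the missing denominator. Events carry dates (Section 11.14) and devices log sessions (Section 11.15), so time-based rates can be computed from planned data. For stimulation-related events, observation through treatment and an exit visit already covers exposure to the device.

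Third, several stronger readings do not hold:
- A reader might infer that a faster-weaning arm would look safer only because it was watched for less time. The bias needs a difference in weaning speed, and Section 3.1 lists complications of ventilation that fewer ventilator days could truly reduce. The last calculation shows both effects together.
- A reader might compare one participant seen for 20 days with one seen for 44. At 2% per day that is 1 − exp(−0.4) = 33% versus 1 − exp(−0.88) = 59%. These are two individuals; the arm-level case above is about 40% versus 29%.
- A reader might infer that any return to ventilation is missed. A return within 72 hours is not weaning success, so it falls before withdrawal for weaning. Only later events lack a scheduled capture.

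**Conclusion.** The point holds in conditional form. Followed as written, the schedule gives shorter adverse-event observation to those who wean, and the planned table does not state how it allows for this. If the arms wean at different speeds, the table may favour the faster arm with equal daily risk: by a risk ratio of about 0.69 to 0.78 for medians of 30 versus 15 days, and 0.92 to 0.95 for 30 versus 25. If they wean equally, there is no bias.

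All hazards and weaning times are assumptions, and the model takes the hazard as constant. With 13 per arm the shift is small next to chance, and no comparative test of adverse events is specified. What is affected is the interpretation of a descriptive safety table, together with the capture of serious events after the exit visit. It is worth changing because the repair is cheap.

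**What to change.** - **Section 17 (and the Synopsis):** define the denominator of the rate. Report adverse events per participant-day of observation by arm and, for stimulation-related events, per stimulation session, beside the patient counts. Show total observed days and sessions for each arm.
- **Section 13.2.1:** state that serious adverse events are collected from the hospital record to Day 45 for every randomised participant who has not withdrawn consent, including those who have weaned.

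The rates use dates and session logs that are already planned. The added cost is a short chart check at Day 45 for participants who left early, and records may be incomplete for those discharged. Treatment, study visits and sample size do not change. Person-time rates remove the imbalance fully only if the daily risk is roughly constant, which is a reason to make both changes.
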